## 12.3 Annex 3 – Additional information

### 12.3.1 Terms to be used for mapping of outcomes

**Table 12-1 Terms to be used to identify cases with the outcomes of interest**

Outcome of interest	Terms to be used	Comments
Angioedema	ICD-9/-10CM/ICD-10GM/Read/ICPC codes corresponding to angioedema, angioneurotic edema, Quincke edema, or any other synonym Allergic oedema, Anaphylactic reaction, Anaphylactic shock, Anaphylactoid reaction, Anaphylactoid shock, Angioedema, Bronchial oedema, Circumoral oedema, Endotracheal intubation, Epiglottic oedema, Gastrointestinal oedema, Genital swelling, Gleich's syndrome, Intestinal angioedema, Laryngeal dyspnoea, Laryngeal obstruction, Laryngospasm, Laryngotracheal oedema, Genital oedema, Mouth oedema, Oropharyngeal spasm, Palatal oedema, Penile oedema, Penile oedema, Periorbital oedema, Pharyngeal oedema, Reversible airway obstruction, Scrotal oedema, Scrotal swelling, Skin oedema, Swelling face, Swollen tongue, Tongue oedema, Tracheal obstruction, Tracheal oedema, Upper airway obstruction, Vaginal oedema, Visceral oedema, Vulval oedema, Vulvovaginal swelling	Primary analysis (' narrow ' definition)  Sensitivity analysis including additional terms on top of the above (' broad ' definition)  Specifically excluded [because too unspecific, risk of too many false positives]: Endotracheal intubation, Reversible airway obstruction, Skin oedema, Upper airway obstruction  'Endotracheal intubation' to be used however, in the context of assessing severity of angioedema (if available/feasible)
Hypotension	Hypotension, Blood pressure decreased, Orthostatic hypotension, Dizziness, Postural dizziness, Presyncope, Syncope	Specifically excluded [because too unspecific, risk of too many false positives]: Depressed level of consciousness, Loss of consciousness  No BP measurements to be included to identify cases of hypotension  Sensitivity analysis for syncope (as a proxy for severe hypotension)
Hyperkalemia	Hyperkalemia, Blood potassium increased	Include lab values for potassium measurements; definition: K + >5.4 nmol/l
Hepatotoxicity	Acute hepatic failure, Drug-induced liver injury, Hepatic failure, Hepatic necrosis, Acute hepatitis, Fulminant hepatitis, Toxic hepatitis, Hepatocellular injury, Hepatorenal failure, Hepatotoxicity, Liver injury, Hepatic encephalopathy	--

---

Renal impairment	Acute kidney injury, Acute nephropathy, Acute prerenal failure, Anuria, Azotaemia, Dialysis, Toxic nephropathy, Renal failure, Renal impairment	--
-------------------------	---	----

---

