## 5 Rationale and background

Sacubitril/valsartan (active substances sacubitril and valsartan, ATC code C09DX04; product name Entresto®) exhibits a novel mechanism of action of an angiotensin receptor neprilysin inhibitor (ARNI) by simultaneously inhibiting neprilysin (neutral endopeptidase; NEP) via LBQ657, the active metabolite of the prodrug sacubitril, and by blocking the angiotensin II type-1 (AT1) receptor via valsartan. The complementary cardiovascular benefits of sacubitril/valsartan in HF patients are attributed to the enhancement of peptides that are degraded by neprilysin, such as natriuretic peptides (NP), by LBQ657 and the simultaneous inhibition of the effects of angiotensin II by valsartan ([Vardeny et al 2014](#)).

In the main randomized controlled trial conducted for sacubitril/valsartan (the PARADIGM-HF trial) which included more than 8,400 HF patients with New York Heart Association (NYHA) class II-IV (ejection fraction  $\leq 40\%$ ), sacubitril/valsartan significantly reduced cardiovascular mortality and the risk of hospitalization by approximately 20%. It also significantly decreased the symptoms and physical limitations associated with HF compared to treatment with the ACEI enalapril, while showing a similar safety profile ([McMurray et al 2014](#)).

Based on this pivotal trial, sacubitril/valsartan (Entresto®) was approved in 2015 in the United States (US), the EU and various other countries. In the EU, sacubitril/valsartan (Entresto®) is approved for the treatment of adult patients with symptomatic chronic heart failure and a reduced ejection fraction.

This study aims to assess the risk for angioedema associated with sacubitril/valsartan in a real-world setting, as well as the risk for several other important identified or potential risks currently listed in the Entresto® Risk Management Plan (RMP) including hypotension, hyperkalemia, hepatotoxicity, and renal impairment.

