#### 7.3.2.1 Angioedema

Angioedema is characterized by non-pitting edema of the dermis and subcutaneous layers. The most common sites of involvement are the tongue, lips, face, and throat; however, swelling can also occur in the extremities, genitalia, and viscera. Life-threatening airway swelling can also occur ([Lewis 2013](#)).

For angioedema, case validation of a random sample will be performed across databases (where possible) to assess the positive predictive value (PPV) of the identification algorithms. If the PPV is below 80% we will aim to validate all cases if that is feasible and informative.

Two definitions will be used:

*Narrow*: angioedema events identified through disease codes [ICD-9/-10 CM, ICD-10 GM, ICPC, Read] specific for angioedema

*Hypersensitivity reaction*: including symptoms not necessarily specific to angioedema but indicative of potential angioedema events

Code lists and identification algorithms (e.g., with confirmatory treatments such as corticosteroids, epinephrine, or antihistamines) were created in close collaboration with the data partners and will be described in the statistical analysis plan (SAP).

For individual terms planned to identify cases with angioedema, see Annex 3 Section 12.3.1 [Table 12-1](#).

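### The broad angioedema list pools airway terms with genital, gastrointestinal and visceral oedema terms that can also record fluid overload in heart failure, so the broad rate and the 'FNR' should be reported by term group

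*Protocol*

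**What the plan says.** Protocol section 7.3.2.1 gives angioedema two definitions. The narrow one uses codes specific for angioedema and is primary. The second is described as "including symptoms not necessarily specific to angioedema but indicative of potential angioedema events", and Table 12-1 (section 12.3.1) gives its role as "Sensitivity analysis including additional terms on top of the above".

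Table 12-1 takes four terms out of the second list because they would produce too many false positives: "Endotracheal intubation, Reversible airway obstruction, Skin oedema, Upper airway obstruction". None of these is genital or visceral. The list keeps "Genital oedema, Mouth oedema, Oropharyngeal spasm, Palatal oedema, Penile oedema", "Scrotal oedema, Scrotal swelling" and "Vaginal oedema, Visceral oedema, Vulval oedema, Vulvovaginal swelling", along with genital swelling and gastrointestinal oedema. Section 7.3.2.1 gives the reason for including such sites: in angioedema "swelling can also occur in the extremities, genitalia, and viscera".

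Three further places bear on the point:

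- Section 7.6.2 selects diagnostic codes that match the terms in Table 12-1, although section 7.3.2 calls the annex an initial list.
- Section 7.1.2 (objective 3) assessed the event algorithms and harmonised the codes on rates in the general adult population.
- Section 7.7.1.2.3 takes the proportion of true angioedema among the hypersensitivity reactions, calls it the false negative rate, and uses it to estimate what the narrow definition missed.

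**The concern.** Heart failure is an inclusion criterion (section 7.2.4), so every patient is at risk of fluid overload. That genital, gastrointestinal or visceral oedema can be recorded for that reason is clinical reasoning. The protocol does not say it of these terms, though section 5.4 recognises congestion of the liver in heart failure. The reason for dropping *Skin oedema* could apply equally to the terms that were kept. A term with few false positives in general adults may have many in this cohort. No section considers this for the oedema terms, and none separates events recorded together with decompensation.

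Two outputs are exposed. The first is the broad incidence rate in each cohort. Section 7.7.1.2.2 applies propensity score overlap weighting only to the exploratory hazard ratios, so a reader who sets the broad rates of cohorts 1 to 4 side by side has no adjustment for severity of heart failure. Section 7.1.2 says severity is recorded for only about 10-20% of patients in the databases that hold it. The second is the 'FNR', which informs how far the narrow primary rate can be trusted. Congestion codes enlarge its denominator.

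**Working it through.** **Plan's own figures.** Section 7.5 assumes 2.9 per 1,000 patient-years (PY) on ACEI and a rate ratio of 1.9. The product is 2.9 × 1.9 = 5.51, stated as 5.5. For 132 cases in 24,000 PY the rate is 5.50 per 1,000, and the exact Poisson 95% interval is 4.60 to 6.52. The stated 5.5 (4.6 to 6.5) reproduces. It concerns the narrow definition and is not in question.

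**Broad rates compared informally.** Let I be the true ACEI angioedema rate, F the rate of congestion-coded false positives on ACEI, and r the ratio of that false-positive rate, sacubitril/valsartan to ACEI. With a true ratio of 1.9,

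broad ratio = (1.9·I + r·F) / (I + F).

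Only F/I matters, so the result is the same at I = 2.9 (section 7.5) and at I = 1.0 (the interim ACEI rate in section 5.1). The documents give neither F nor r; both are assumptions. r = 0.8 takes the roughly 20% reduction in section 5 as a proxy. r = 1.2 stands for channelling to more severe heart failure (section 7.9).

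| F/I | r = 0.8 | r = 1.0 | r = 1.2 |
|---|---|---|---|
| 0 | 1.90 | 1.90 | 1.90 |
| 1 | 1.35 | 1.45 | 1.55 |
| 2 | 1.17 | 1.30 | 1.43 |
| 4.5 | 1.00 | 1.16 | 1.33 |
| 10 | 0.90 | 1.08 | 1.26 |

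For example, at F/I = 2 and r = 0.8: (1.9 + 1.6)/3 = 1.17. At F/I = 4.5: (1.9 + 3.6)/5.5 = 1.00. With r = 1.2 an excess remains, but part of it is decompensation.

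**The 'FNR'.** Take the plan's 132 narrow cases as true. Assume that the hypersensitivity events outside the narrow definition comprise 50 true missed cases and 50 other non-cases.

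- No congestion codes: 'FNR' = 50/100 = 50%.
- 500 congestion codes added: 'FNR' = 50/600 = 8%.
- Share of true cases missed by the narrow definition, in both settings: 50/(132 + 50) = 27%.

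The 'FNR' moves sixfold while the quantity of interest does not move. Multiplied by its own event count it still recovers the number missed: 0.50 × 100 = 50 and 0.0833 × 600 = 50. What is lost is precision. If n events are validated at random (finite-population correction ignored), the standard error of the missed-case count is:

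- no congestion codes: 100 × √(0.5 × 0.5/n) = 50/√n;
- pooled with 500 congestion codes: 600 × √(0.0833 × 0.9167/n) = 166/√n, or 3.3 times as large;
- two strata, n/2 from each, all true cases in the first stratum of 100: 100 × √(0.25/(n/2)) = 71/√n, or 1.4 times as large.

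The last line is the favourable case for stratifying. If true cases also lie in the second stratum, the gain is smaller.

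**The case against.** The strongest reply is that little depends on the broad definition. It is a sensitivity analysis, section 7.7.1.2.2 restricts every hazard ratio to the narrow definition, and no broad rate ratio is planned. Section 6.3 already labels all comparisons exploratory. This stands. A reader might infer that the retained terms could hide a real increase in angioedema. The documents do not support that, because an increase captured by the narrow codes would still show in the primary rates and the hazard ratios.

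A reader might also infer that the bias favours sacubitril/valsartan, since section 5 reports that in the pivotal trial "sacubitril/valsartan significantly reduced cardiovascular mortality and the risk of hospitalization by approximately 20" per cent. Section 7.9 points the other way: the drug may be channelled to patients with more severe heart failure, which would put more congestion codes in its cohorts. The direction is open.

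It can further be said that the terms name recognised angioedema sites while *Skin oedema* names none, that low specificity is admitted, that a validation study is under way, and that algorithms with confirmatory treatments may be in the SAP. These points explain the choice and may soften its effect. They do not remove it. A recognised site does not make a code specific in heart failure. Confirmatory treatment appears in section 7.3.2.1 only as an example, with no rule for these terms. The protocol states no split of the validation result by term group. Calling the annex an initial list carries limited weight when section 7.6.2 selects codes from it.

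**Conclusion.** The point holds as a limited one about interpretation. The broad list keeps terms that can record fluid overload in a cohort made up wholly of heart failure patients, and its harmonisation on general-population rates could not show this. The primary rate and the hazard ratios are untouched. The broad rates, read across cohorts without adjustment, and the pooled 'FNR' can be driven by congestion codes.

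The size is not known. Complete attenuation of a true ratio of 1.9 needs about 4.5 congestion codes per true ACEI case together with r = 0.8, and neither figure is in the documents. The 'FNR' result rests on assumed counts. It shows only that a diluted share misleads if read directly as the share of cases missed, and that pooling costs precision. The conclusion also assumes that these codes are sometimes used for congestion, which is clinical reasoning that the validation study can confirm or refute. It is a worthwhile, cheap improvement.

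**What to change.** 1. Report the broad sensitivity rate, by cohort and database, in two parts: (i) face, mouth, pharynx, larynx, airway and anaphylaxis terms; (ii) genital, gastrointestinal and visceral oedema terms. Assign in advance the terms that do not fall clearly into either part, such as allergic oedema, Gleich's syndrome and intestinal angioedema.
2. Stratify the hypersensitivity validation sample by these groups and report the validated true share in each.
3. Estimate missed cases as the true share times the event count within each group, then sum. Do not read the share in section 7.7.1.2.3 as a false negative rate; the share of cases missed is missed cases divided by all true cases.
4. Restricting group (ii) to events with a confirmatory treatment and no concurrent decompensation record should be at most an extra sensitivity row, because it discards true cases.

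The cost is some programming and one table. Steps 1 to 3 lose no cases and leave the primary analysis unchanged. If the validation sample has already been drawn, its results can still be tabulated by group, with less precision where a group is thinly sampled.

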#### 7.7.1.2.3 Sensitivity analyses

Details on sensitivity analyses will be specified in the SAP, including potential safety event misclassification, potential COVID-19 impact, and the impact of duration of prevalent ACEI use in a subset of cohort 3. In the (ongoing) validation study, the proportion of true angioedema cases among the hypersensitivity reactions is calculated as the false negative rate (FNR). The FNR will be used to estimate what proportion of angioedema events might have been missed with the narrow definition of angioedema.

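### Table 12-1 nests the narrow angioedema codes inside the sensitivity set, but the missed-case estimate in section 7.7.1.2.3 needs hypersensitivity records with no narrow code

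*Protocol*

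**What the plan says.** The Protocol describes the second angioedema definition in several places.

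- **Section 7.3.2.1** gives two definitions. Narrow means "angioedema events identified through disease codes" that are specific for angioedema. Hypersensitivity reaction is described as "including symptoms not necessarily specific to angioedema but indicative of potential angioedema events". Nothing there says that the second contains the first. Section 7.3.2 labels them as the primary and the sensitivity analysis.
- **Table 12-1 (section 12.3.1)** gives the narrow set as "codes corresponding to angioedema, angioneurotic edema, Quincke edema, or any other synonym". It then describes a second set, labelled 'broad', as "Sensitivity analysis including additional terms on top of the above". The additional list contains both angioedema and intestinal angioedema.
- **The same row** comments: "Specifically excluded [because too unspecific, risk of too many false positives]: Endotracheal intubation, Reversible airway obstruction, Skin oedema, Upper airway obstruction". All four of those terms also stand in the column of terms to be used. The comment adds that intubation is kept for judging severity where feasible.
- **Section 7.7.1.2.3** says that in the validation study "the proportion of true angioedema cases among the hypersensitivity reactions is calculated". It calls this share the false negative rate and will use it to estimate how much angioedema the narrow definition may have missed.
- **Section 7.6.2** has diagnostic codes selected to match the terms in Table 12-1. Section 7.3.2 calls the annex list initial, and section 7.3.2.1 leaves code lists and algorithms to the SAP.
- **Section 7.1.2**, on feasibility objective 3, still calls the two angioedema definitions narrow and broad.

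**The concern.** The text and the table describe two different sets under two labels. In the text, hypersensitivity reaction stands next to the narrow definition. In the table, the sensitivity set is a union that contains every narrow case.

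For an incidence rate either choice could be defended, provided it is stated. For the missed-case estimate only one works: a patient with a narrow angioedema code has been counted by the primary definition and cannot have been missed by it. If the validation share is taken in the table's set, part of its numerator and denominator consists of cases the primary analysis already has.

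At stake is the one planned quantity that tells a reader how far the primary safety event is under-ascertained. The sensitivity incidence rate would also mean different things depending on which passage a data partner followed.

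**Working it through.** **1. Compare the term lists in Table 12-1.**

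- The additional angioedema list has 40 entries, 39 of them distinct (one genital oedema term appears twice).
- One entry is angioedema, which is a narrow term. So even the additional terms taken alone overlap the narrow set.
- All 4 of the terms called excluded are in the list. In the hypotension row, neither of the 2 excluded terms is listed as used, so listing excluded terms is not the table's convention.
- Removing the four leaves 39 − 4 = 35 distinct terms. Removing angioedema leaves 34. Removing intestinal angioedema, if it is already a narrow synonym, leaves 33.

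**2. Set out what section 7.7.1.2.3 requires.** Let N be the number of narrow records and p their true share (the PPV). Let H be the number of hypersensitivity records without a narrow code and h their true share.

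- Share in a separate group: h.
- Share in the table's union: (N·p + H·h)/(N + H).
- Difference, union minus separate: N·(p − h)/(N + H).
- Proportion of all true cases that the narrow definition missed: H·h/(N·p + H·h).

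The union share is a weighted average of p and h. It exceeds h whenever narrow codes are more often true than non-specific ones, and it depends on N and p, which say nothing about missed cases.

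**3. Illustrate with assumed inputs.** The Protocol gives N only indirectly. The fourth interim rate of 0.7 per 1,000 PY (section 5.1) times the planned 24,000 PY (section 7.5) is 16.8, about 17. H and h are not in the documents. I assume h = 5% and H = 50 or 170. I take p = 80%, which in section 7.3.2.1 is a validation threshold and not an expected value. True narrow cases are then 17 × 0.8 = 13.6.

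| | H = 50 | H = 170 |
|---|---|---|
| True cases without a narrow code, H·h | 2.5 | 8.5 |
| Share in the separate group | 5% | 5% |
| Share in the union | 16.1/67 = 24% | 22.1/187 = 12% |
| Proportion missed | 2.5/16.1 = 15.5% | 8.5/22.1 = 38.5% |

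The union share moves in the opposite direction to the proportion missed: it falls from 24% to 12% while the proportion missed rises from 15.5% to 38.5%. Read as the proportion missed, it is too high in one column and too low in the other. The separate share is not itself the proportion missed either, but with H and the narrow counts it can be converted. The union share first has to be stripped of its narrow cases.

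**4. Check what is untouched.** The primary rate and the exploratory hazard ratios use the narrow definition only (sections 7.3.2 and 7.7.1.2.2). The study-size figure reproduces: 132/24,000 PY is 5.5 per 1,000 PY with an exact Poisson interval of 4.60 to 6.52, against the stated 4.6 to 6.5. It does not depend on this point.

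**The case against.** **The text already implies a separate group.** Section 7.7.1.2.3 speaks of hypersensitivity reactions, not of the broad set, and its purpose presupposes records the narrow definition did not catch. This stands in part. A reader might infer from Table 12-1 that the sensitivity counts certainly include primary cases. The documents do not support that: sections 7.3.2.1 and 7.7.1.2.3 point the other way, so the Protocol contradicts itself without settling on the union.

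**The annex is only an initial list, with detail left to the SAP.** That is true of the code lists. It does not reconcile two different definitions within the Protocol, and section 7.6.2 makes the table's terms the basis for code selection.

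**A nested broad definition is a normal sensitivity analysis.** Agreed for an incidence rate. It does not carry over to an estimate of what the narrow definition missed.

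**The excluded terms are resolved in the same row.** Agreed. A reader might infer that a patient intubated for any reason would count as a case. The comment rules that out and explains why intubation is listed. What remains is untidiness.

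**No size can be claimed.** A reader might set the union shares above against 5% and infer that missed angioedema is overstated 2.4 to 4.8 times (12/5 and 24/5). That does not follow. H and h are assumed, and the comparison is between two true shares, whereas the target is the proportion missed, against which the union share errs in either direction.

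**Conclusion.** The conflict stands in the current text. Table 12-1 defines the angioedema sensitivity set as narrow codes plus additional terms and repeats angioedema among the latter. Sections 7.3.2 and 7.3.2.1 define a separate hypersensitivity group, and section 7.7.1.2.3 needs one.

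If the table's set were used for the validation share, cases already counted would enter the missed-case estimate. That the union share exceeds the separate share rests only on narrow codes having the higher PPV. Neither the size of the distortion nor its direction relative to the proportion missed can be derived from the documents.

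The effect is confined to the hypersensitivity incidence rate and the missed-case estimate. The passages should be reconciled before the validation result is used in the final report.

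**What to change.** - In section 7.3.2.1 and Table 12-1, use one label and one definition: hypersensitivity reaction is a record matching the additional terms in a patient with no narrow code for that event. Bring the wording in sections 7.1.2 and 7.7.1.2.2 into line.
- Remove angioedema from the additional list. State whether intestinal angioedema already counts as a narrow synonym and, if so, remove it too. It should not be moved into the primary definition by default while validation is ongoing (section 7.6.1).
- Compute the quantity in section 7.7.1.2.3 only in this non-overlapping group.
- If a narrow-or-hypersensitivity rate is wanted, report it as a separately named count.
- As tidy-up, take the four excluded terms and the repeated entry out of the case-identification list, keeping endotracheal intubation only as the severity marker the row already describes.

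The cost is table and section wording plus a flag in the event file for a narrow code at the same event. No new data are needed.
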